9.6.3 Audits and inspections

Authorized representatives of Sponsor, or a Competent Authority may perform audits or inspections at the investigational site. The purpose of an audit or inspection is to systematically and

Document	Doc. id.	Version	Page	
Clinical investigation Plan / Investigation code- AI-DSMM/	GR 21- 023	01	36 (52)	

independently examine all investigation-related activities and documents, to determine whether these activities were conducted, and data were recorded, analysed, and accurately reported according to the CIP, EN ISO 14155 and any other applicable regulatory requirements.

The site Investigators are required to inform the Sponsor-Investigator immediately of an inspection requested by a Competent Authority or IEC.

9.6.4 Case Report Forms

Case Report Forms must be completed and signed by authorized personnel for each included subject.

All data must be entered in English. The CRFs should always reflect the latest observations made during the subject's participating in the investigation. Therefore, the CRFs should be completed as soon as possible during or after the subject's visit.

The Investigator must verify that all data entries in the CRFs are accurate and correct by signing the completed CRF.

The completed CRFs should be made available for checking of completeness and accuracy by the Monitor as agreed in advance.

9.6.5 Source Data

A separate source data document will be generated for the investigational site before start of enrolment, specifying the location of the source of derived information appearing in the CRF. This document must be signed by the Sponsor-Investigator and the Monitor to confirm agreement before the start of recruitment.

The Investigator should guarantee access to source documents to the Monitor, Competent Authorities and the IECs, if required.

9.6.6 Training of investigation staff

In connection to Site initiation visit, all sites will be trained on the ISO 14155 (GCP training) via a video, the sites will have time to ask questions during a Q&A. Before inclusion of the first investigational subject the Monitor/sponsor will perform an Initiation Visit at the investigational site, this may be done remotely, if applicable. The requirements of the CIP and related documents will be reviewed and discussed, and the investigational staff will be trained in any investigation specific procedures and system(s) utilised. A Site Initiation slide deck will be reviewed with the site, to

Document	Doc. id.	Version	Page	
Clinical investigation Plan / Investigation code- AI-DSMM/	GR 21- 023	01	37 (52)	

ensure for example Informed Consent, medical record keeping, and safety reporting and timeline are reviewed in detail with the sites. The training will include IMD usage and mitigation of residual risks.

It is the responsibility of the Principal Investigator to ensure that all personnel involved in the investigation are fully informed of all relevant aspects of the investigation and have detailed knowledge of and training in the procedures that are to be executed by them. Any new information of relevance to the performance of this investigation must be forwarded to the staff involved in a timely manner. [name] and [name] are the PIs for the investigation and have oversight at the 30 other clinical investigational sites. A more detailed information will be given in the document 07e_Site structure, GCP Resources and PI oversight_1.0_20Jan2022.

The Investigator will keep a list of all personnel involved in the investigation together with their function and investigation related duties delegated. A Curriculum Vitae (CV) will be available for all staff delegated investigation-specific duties.

9.7 Statistical methods and determination of sample size

9.7.1 General

Data from all variables will be presented by means of descriptive statistics and all data will be presented by line listings.

Descriptive statistics implies providing the number of observations, number of missing data, minimum, median, maximum, mean and standard deviation for all continuous and ordered categorical data. Binary data and non-ordered categorical data will be presented by count and percentage in each category.

9.7.2 Demographics and other baseline characteristics

Demographics and other baseline characteristics will be presented using descriptive statistics.

Document	Doc. id.	Version	Page	
Clinical investigation Plan / Investigation code- AI-DSMM/	GR 21- 023	01	38 (52)	

9.7.3 Analysis of clinical performance

9.7.3.1 Primary Objective and Endpoint

The primary objective of the investigation is to determine the diagnostic precision of the device; to answer at which level the AI tool Dermalyzer can identify malignant melanomas among cutaneous lesions that are assessed in clinical use due to any degree of malignancy suspicion.

The primary endpoint will be measured as the true proportion; by testing if the device based on artificial intelligence (AI) gives correct results as compared with the result of the lesion analysis (the final classification by PAD) in at least a certain proportion (π) of the analyses.

9.7.3.2 Secondary Objective and Endpoint

The primary objectives are to evaluate usability and applicability in clinical praxis of Dermalyzer by users (medical professionals) and to gain an increased knowledge and understanding of how digital tools enhanced co-artificial intelligence can assist physicians with the right support for an earlier diagnosis of malignant melanoma.

The second endpoint will be measured by User questions including System Usability Scale to evaluate the usability and applicability in clinical praxis. In addition to these endpoints, a number of analyses will be done that can be found in the SAP.

9.7.3.3 Exploratory Objective and Endpoint

The exploratory objective is to explore health economic aspects of improved diagnosis support.

The exploratory endpoint will be measured by collecting health economic related information by survey to participating sites.

9.7.4 Analysis of safety

9.7.4.1 Endpoint 1

The main risks identified for similar devices are incorrect diagnosis (false positives and false negatives) due to limitations in the training data set that was used to develop the software. According to the risk management, the only unacceptable risk identified for Dermalytics is that some individuals, including patients with ulcerations (damage to the skin), external modification to the skin, absence of surrounding skin (normal skin around), will be excluded. This is stated in the IFU for

Template Doc. id. Version

CIP Template QMS 12-01- 02
01

Document	Doc. id.	Version	Page	
Clinical investigation Plan / Investigation code- AI-DSMM/	GR 21- 023	01	39 (52)	_

the IMD. The prevalence of incorrect diagnosis will be captured in the primary endpoint analysis, as well as the possibility of reduced risk of missing malignant melanomas (false negatives). The consequences of false negatives will be evaluated by collecting health economic data. To this end, the participating clinicians will be provided a survey with questions on how the use of Dermalytics would affect health economic aspects, such as time to treatment, number of visits to dermatologists and number of excisions.

9.7.5 Analysis data sets

The data will be analysed using three analysis sets:

- · Intention To Treat (ITT)
 - All correctly (i.e., fulfill all entry criteria) included subjects are included in this analysis set.
- · Per Protocol (PP)
 - This is a subset of the ITT analysis set and all patients that are included in the ITT analysis and as well has followed all major procedures in the investigation (to be defined prior to start of the statistical analysis).
- Safety Analysis Set (SAS)
 - o Includes all subjects who have been exposed to the Demlayzer

9.7.6 Determination of sample size

The general practitioner (GP) will only include subjects in the investigation with lesions where melanoma cannot be ruled out. All lesions where melanoma cannot be ruled out will be sent for an analysis (final classification) to confirm – or not confirm – if the suspected melanoma is a melanoma or not. Each lesion where melanoma cannot be ruled out will be analysed by the IMD and the IMD will classify each lesion where melanoma cannot be ruled out as "Low Risk of being a melanoma" (Low) or "High risk of being a melanoma" (High).

In Table 1 the possible outcomes are described and (A+D)/(A+B+C+D) is the proportion of correct classifications by the IMD.

Template Doc. id. Version

CIP Template QMS 12-01- 02
01

Document Doc. id. Version Page

Clinical investigation Plan / Investigation code- AI-DSMM/ GR 21- 023 01 40 (52)

Table 1 Outcome (m = number of patients) for a binary variable where two groups of observations are linked together.					
			The Al device		
		High	Low	Total	
Final classification	Melanoma	А	В	A+B	
	Not melanoma	С	D	C+D	
	Total	A+C	B+D	A+B+C+D	

The expected value of (A+D)/(A+B+C+D) is denoted π and then the hypotheses of interest are

 H_0 : $\pi \leq \pi_0$

 H_1 : $\pi > \pi_0$

The null-hypothesis (H₀) will be rejected if the one-sided p-value is less than a. If $\pi = \pi_1$ the power to reject H₀ should be β .

Typically, a = 2.5 % and β = 80 % or 90 %. The p-value will be calculated using the exact Binomial test.

In a successful investigation H_0 is rejected and then H_1 is accepted.

Document Doc. id. Version Page

Clinical investigation Plan / Investigation code- AI-DSMM/ GR 21- 023 01 41 (52)

In Table 2 the needed number of lesions is presented based on the formula above and for statistical power 90%.

Table 2	Number of lesions where melanoma cannot be ruled out needed to achieve 80% power to reject (i.e. get a one-sided p-value less than 2.5%) the null-hypothesis by proportions to be rejected (i.e., π_0) and by assumed true proportions (i.e. π_1). Calculated by Sample Size a single proportion V01.xls.					
True Proportion (π ₁)		Р	roportion to b	oe rejected (π	:0)	
(71)	50%	60%	70%	80%	90%	95%
55%	783					
60%	194					
65%	85	742				·
70%	47	182				
75%	29	78	638			
80%	20	43	153			·
85%	14	26	64	471		·
90%	10	17	34	108		
95%	7	11	19	42	239	

Document			Doc. id.	Version	Page	
Clinical investigation Plan / Investigation code- AI-DSMM/		GR 21- 023	3 01	42 (52)		
100%	4	6	9	16	35	73

The set expectation of 95% true proportion is based on in-silico experiments on a proprietary dataset of images which found a sensitivity of 95.1 \pm 0.6%.

The accuracy of AI decision support will be measured against gold standard (PAD) as well as against experienced dermatologists and general practitioners (average) and verified at: sensitivity> 95%, specificity> 75%, numbers needed to excise (NNE) <7, positive predictive value (PPV))> 15% and negative predictive value (NPV)> 99.5%. The average sensitivity for general practitioners in previous meta-analyzes is estimated at about 81%.

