3 SYNOPSIS

Title of the clinical investigation

A prospective clinical investigation to assess the diagnostic precision of the artificial intelligence (AI) tool Dermalyzer to identify malignant melanomas in subjects seeking primary care for melanomasuspected *cutaneous* lesions

Investigation code	Investigational Medical Device	IMD classification
AI-DSMM	Dermalyzer	IIb

Intended use

Dermalyzer is a device intended to be used as a decision support system for assessing cutaneous lesions suspected of being melanomas. The input from the device is not intended to be used as the sole source of information for diagnosis. The device should be used in combination with a medical professional assessment of the suspected lesion. Intended to be used by medical professionals. The service does not provide any other diagnosis.

Coordinating/Principal Investigator

[name], assoc.professor, Region Östergötland

Time period for the clinical investigation

Estimated date of first subject enrolled: Q1 2022

Estimated date of last subject completed: Q3 2022

Design of the clinical investigation

This will be a pre-market, prospective, confirmatory, first in clinical setting, pivotal multi-centre, non-interventional clinical investigation to evaluate the clinical safety, performance and benefit of Dermalyzer in patients with cutaneous lesions where malignant melanoma (MM) cannot be ruled out.

Objectives and endpoints

Primary objective

Document	Doc. id.	Version	Page	
Clinical investigation Plan / Investigation code- AI-DSMM/	GR 21- 023	01	9 (52)	_

The primary objective of the investigation is to determine the diagnostic precision of the device; to answer at which level the AI tool Dermalyzer can identify malignant melanomas among cutaneous lesions that are assessed in clinical use due to any degree of malignancy suspicion.

Primary endpoint

The primary endpoint will be measured as the true proportion; by testing if the device based on AI gives correct results as compared with the result of the lesion analysis (the final classification by histopathology (PAD) in at least a certain proportion (π) of the analyses.

Secondary objectives

As secondary objectives a number of analyses will be done.

To evaluate usability and applicability in clinical praxis of Dermalyzer by users (medical professionals)

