8 INVESTIGATIONAL OBJECTIVES AND ENDPOINTS

8.1 Primary objective

The primary objective of the investigation is to determine the diagnostic precision of the device; to answer at which level the AI tool Dermalyzer can identify malignant melanomas among cutaneous lesions that are assessed in clinical use due to any degree of malignancy suspicion.

Template Doc. id. Version

02

Document	Doc. id.	Version	Page	
Clinical investigation Plan / Investigation code- AI-DSMM/	GR 21- 023	01	22 (52)	

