9.3.2 Number of subjects

To reach the target of 239 eligible lesions with a PAD approximately 500 lesions will need to be included, that is up to 500 subjects. The CI needs to be able to analyse 239 PAD verified lesions where at least 12 lesions need to be PAD positive responses (confirmed MM). In case, after 500 subjects/lesions have been evaluated and the 12 positive PAD have not been obtained, further subject enrolment will continue until 12 positive PAD have been reached.

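### The only stated test is on pooled accuracy, about 95% of which is specificity, so rejecting H0 does not by itself show that the device identifies melanomas

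*Combined protocol and SAP*

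**What the plan says.** **Objective.** Section 8.1 sets out "to answer at which level the AI tool Dermalyzer can identify malignant melanomas among cutaneous lesions".

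**Endpoint and test.** The synopsis, 8.1.1 and 9.7.3.1 ask whether the device agrees with histopathology "in at least a certain proportion (π) of the analyses". Section 9.7.6 makes this concrete: "A+D)/(A+B+C+D) is the proportion of correct classifications by the IMD", where A and B are melanomas called High and Low, and C and D are non-melanomas called High and Low. H0: π ≤ π0 is tested by the exact binomial test, one-sided 2.5%. The section adds: "In a successful investigation H_0 is rejected and then H_1 is accepted".

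**Targets.** The same section says accuracy will be "verified at: sensitivity> 95%, specificity> 75%, numbers needed to excise (NNE) <7", together with PPV above 15% and NPV above 99.5%. No hypothesis, interval or decision rule is attached. The synopsis also plans kappa, sensitivity, specificity and predictive values, again without a threshold for success.

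**Planning value.** "The set expectation of 95% true proportion is based on in-silico experiments on a proprietary dataset of images which found a sensitivity of" 95.1 ± 0.6%.

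**Safety.** Section 9.7.4.1 states: "The prevalence of incorrect diagnosis will be captured in the primary endpoint analysis", and it includes missed melanomas there.

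**Numbers.** The synopsis gives 239 lesions, an expected proportion of 95%, 80% power and 12 melanomas. Under 9.3.2, if 500 subjects or lesions have not yielded 12 melanomas, "further subject enrolment will continue until 12 positive PAD have been reached". That sets how many melanomas are collected, not how many must be detected.

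**The concern.** When one class makes up 5% of the sample, overall accuracy says little about how well that class is recognised. The error that matters most for this device is a missed melanoma, and each one costs the statistic no more than one false alarm among 227 non-melanomas. The synopsis calls the investigation confirmatory and pivotal for a device not yet CE-marked, so its formal result is likely to carry weight.

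The test can therefore reject when few or no melanomas are found, and fail to reject when all are found. Since the plan does not say how the test and the listed targets combine, conflicting results would have to be settled after the data are seen.

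**Working it through.** **1. Reproduce the plan's figure.** One-sample proportion, normal approximation, π0 = 0.90, π1 = 0.95, one-sided 2.5%, 80% power:

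n = [(1.960·√(0.90·0.10) + 0.842·√(0.95·0.05)) / 0.05]² = 238.03, rounded up to 239.

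This matches Table 2, and nine other cells checked also reproduce. At 90% power the same formula gives 301, so 239 is an 80% figure, as the caption and synopsis say. No other cell gives 239, which is why π0 = 90% is inferred.

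**2. Rejection rule.** Exact binomial, n = 239, π0 = 0.90:
- P(X ≥ 225) = 0.0162
- P(X ≥ 224) = 0.0293

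So H0 is rejected at 225 or more correct (94.1%).

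**3. Weights.** With 12 melanomas, accuracy = (12/239)·sensitivity + (227/239)·specificity = 0.050·sensitivity + 0.950·specificity.

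**4. Possible results at π0 = 90%.**

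| Melanomas found | Non-melanomas correct | Total correct | p | H0 |
|---|---|---|---|---|
| 0/12 (all 'Low') | 227/227 | 227 | 0.0040 | rejected |
| 0/12 | 225/227 (99.1%) | 225 | 0.0162 | rejected |
| 12/12 | 212/227 (93.4%) | 224 | 0.0293 | not rejected |
| 12/12 | 171/227 (75.3%) | 183 | >0.999 | not rejected |

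With 0/12 found, rejection needs specificity of at least 225/227 = 99.1%. With 12/12 found, it still needs at least 213/227 = 93.8%.

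The last row meets every listed target as a point value: sensitivity 100%, specificity 75.3%, PPV 12/(12+56) = 17.6%, NPV 100%, and NNE 68/12 = 5.7 (taking NNE as 1/PPV, since the plan does not define it).

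**5. Probability of rejecting, by true performance** (12 and 227 lesions, π0 = 90%):
- Sensitivity 50%, specificity 98%: expected correct 6 + 222.5 = 228.5; rejects 92% of the time.
- Sensitivity 95%, specificity 75% (exactly at the two targets): expected accuracy (11.4 + 170.25)/239 = 76.0%; rejects with probability 5×10⁻¹⁴.
- Sensitivity 95%, with specificity 90%, 95% and 96%: rejects 2%, 78% and 94% of the time.

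**6. Dependence on π0.** Critical values for π0 = 50, 60, 70, 80, 90 and 95% are 136, 159, 182, 204, 225 and 234. All-'Low' (227) rejects at each of the first five but not at 95%. The 12/12 with 171/227 result (183) rejects at 70% or below and fails at 80% and above.

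**7. What 12 melanomas can show.** Exact two-sided 95% limits: 12/12 has a lower limit of 73.5%; 11/12 (91.7%) has 61.5% to 99.8%. A device with true sensitivity 95% finds all 12 with probability 0.95¹² = 54%.

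**The case against.** **The plan does measure melanoma detection.** This is right. Table 1 keeps B and C apart, the synopsis plans sensitivity, specificity, predictive values and kappa, and 9.7.6 lists targets. An all-'Low' device would have sensitivity 0%, NPV 227/239 = 95.0% and kappa 0.00; 12/12 with 212/227 would have kappa 0.59. A reader of the full results would not be misled. What remains is that none of these measures has a test or any stated link to success.

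**Rejection may be meant as necessary, not sufficient.** A reader might infer that the plan would declare success with no melanoma found. The documents do not support that: the success sentence says what happens in a successful investigation, not that rejection is enough, and the targets stand in the same section. But if rejection is only necessary, a result meeting every target can still fail. The plan does not say which reading holds.

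**π0 = 90% is inferred.** It is, and the 12/12 failures depend on it. At π0 = 80%, 224/239 would reject (p about 2×10⁻⁹). The all-'Low' result is less sensitive to this, holding from 50% to 90%.

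**The 0/12 case is extreme.** It needs at least 99.1% specificity. The 50%/98% device is less extreme, and the 12/12 failure covers every specificity from the 75% target up to just below 93.8%.

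**Missed melanomas are named in 9.7.4.1.** True, and a tabulation would show them. Only the test statistic merges B with C.

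**The SAP may settle it.** Section 9.7.3.2 refers further analyses to a SAP. No separate SAP text was available, so a rule there cannot be excluded.

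**Conclusion.** The point holds in this form: in the text available, the only test and the only success statement concern pooled accuracy, and rejecting H0 does not by itself answer the primary objective. At the inferred π0 of 90%, an all-'Low' device rejects (p = 0.0040), while a result with every melanoma found and every listed target met as a point value does not (183/239). The all-'Low' result rests on 12 melanomas in 239 lesions and any tabulated π0 from 50% to 90%; the 12/12 result needs π0 of 80% or more.

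A reader might also infer that the accuracy test and the targets are incompatible. They are not: a device at 95%/95% passes the test 78% of the time, and one at 95%/96% passes 94% of the time. The defect is the missing rule joining them, made worse by an unstated π0 and by an expected accuracy taken from an in-silico sensitivity. It should be corrected before any conclusion is drawn from the test.

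**What to change.** In 9.7.6, state π0 and add text such as:

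> Rejecting H0 for overall accuracy is not sufficient to call the investigation successful or to claim that the device identifies melanomas. Sensitivity A/(A+B) and specificity D/(C+D) are reported with the primary result, each with an exact two-sided 95% CI, together with kappa, PPV, NPV and NNE. The targets in this section are judged on point estimates, with CIs reported beside them. No claim of melanoma identification is made unless the sensitivity target is met. With 12 melanomas, sensitivity is estimated, not confirmed: 12/12 has a lower limit of 73.5%, and 11/12 (91.7%; 61.5% to 99.8%) misses the target.

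Also in 9.7.6, state that the 95% expected accuracy came from a sensitivity figure and that the accuracy test can fail for a device meeting the targets. In 9.7.4.1, report false negatives (B) and false positives (C) separately. Carry the wording to the synopsis, 8.1.1 and 9.7.3.1, and qualify the synopsis's description of the investigation as confirmatory so that it does not extend to sensitivity.

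**Cost.** An amendment under 11.1, with ethics committee and Competent Authority approval if it counts as substantial. No added patients, procedures or data: A to D are already collected. The sensitivity claim becomes more modest, and with 12 melanomas even a truly 95%-sensitive device meets the target only 54% of the time. Replacing accuracy as the primary test is a possible further step, but this point does not require it.

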When the subject has been fully examined and receives the final tumor diagnosis from the histopathology/PAD results (melanoma/non melanoma), the degree of agreement between the PAD and the outcome of the AI SW decision support is calculated with the Kappa-analysis and the diagnostic accuracy to be able to distinguish melanoma from non-melanoma in the form of sensitivity and specificity as well the positive and predictive value. The corresponding comparison is performed from the examining investigators' estimated clinical degree of suspicion, as well as the diagnostic accuracy when both the PAD and the AI decision support are weighted together (i.e. in cases where the investigator and the decision support are in agreement in their assessment). The clinical investigation will collect information from the users, how participating users (investigators at the site) experience the usability of the AI SW decision support and attaching applications, from short surveys including the validated System Usability Scale.

Use the same overall description given in Section 9.1.

Duration of exposure to the Investigational Medical Device

The subjects will not be in any direct contact with IMD Dermalyzer.

Duration of subjects' involvement in the investigation

The subjects will only perform 1 visit at a primary care centre to assess the cutaneous lesion(s).

Clinical performance assessments

The subject will be examined according to clinical routine. The cutaneous lesions where MM cannot be ruled out (study lesions) will be photographed with a digital dermatoscope. The digital image will then be able to be instantly uploaded to the study's AI enhanced web application (Dermalyzer), where the AI algorithm performs the image analysis within a few seconds.

Template Doc. id. Version

02

CIP Template QMS 12-01-

Document	Doc. id.	Version	Page
Clinical investigation Plan / Investigation code- AI-DSMM/	GR 21- 023	01	12 (52)

Clinical safety assessments

All considered reportable events in accordance with MDR, will be captured. The subject included in the investigation will follow the standard of care. The use of the AI will not influence the subject or the medical care of the subject.

Statistical methods

The sample size of at least eligible 239 lesions is calculated by an expected true proportion of 95% with 80% power. The estimated frequency of actual found malignant melanoma is 4.65% (or 12 MM out of 239 lesions).

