9.3.4 Inclusion criteria

For inclusion in the investigation, subjects must fulfil all the following criteria:

- 1. Patients ≥18 years
- 2. Patients attending a healthcare facility with at least 1 suspicious skin lesion where MM cannot be ruled out.
- 3. Willingness and ability to provide informed consent.

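### The primary exact binomial test and the 239-lesion size assume independent lesions, which the design does not secure, so the 2.5% level and 80% power are not assured

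*Combined protocol and SAP*

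**What the plan says.** Section 9.7.6 defines the primary parameter as the overall proportion of lesions that the device classifies correctly, (A+D)/(A+B+C+D), and fixes the test: "The p-value will be calculated using the exact Binomial test". Table 2 counts lesions, and its title sets the one-sided level ("i.e. get a one-sided p-value less than 2.5" per cent). The synopsis states: "The sample size of at least eligible 239 lesions is calculated by an expected true proportion of 95% with 80% power".

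Subjects need not contribute a single lesion. Section 9.3.4 admits patients "with at least 1 suspicious skin lesion where MM cannot be ruled out", with no upper limit. Section 9.1 has the investigator image each study lesion, and Table 9.1 records how many there are. Section 9.3.2 expects that "approximately 500 lesions will need to be included, that is up to 500 subjects", which permits one lesion per subject but does not require it.

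The unit is not consistent. The title of Table 1 reads "Outcome (m = number of patients) for a binary variable", Table 2 counts lesions, and the analysis sets in section 9.7.5 are defined by subject.

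The synopsis plans about 30 primary care centres. Section 9.4.9 gives each site its own phone and names two dermatoscope models. The text contains no ICC, design effect, clustered method, one-lesion rule or sensitivity analysis for this.

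**The concern.** The exact binomial test needs independent trials with a common success probability. Lesions on one person share skin type, naevus pattern, operator, phone and dermatoscope, so the device's errors on them are plausibly positively correlated. Lesions from one site share equipment and practice. Positive correlation makes the count of correct results more variable than the binomial distribution allows. A rule set from that distribution then rejects too often under the null hypothesis and has less power than planned under the alternative.

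This matters because the study is described as pivotal and confirmatory, and section 9.7.6 makes one rejection of the null hypothesis the criterion for success.

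**Working it through.** **Inputs from the documents.** One-sided level 2.5% and power 80% (Table 2 title; synopsis), π1 = 95% (section 9.7.6) and 239 lesions. The text never names π0. It is inferred as 90%, because 239 is the Table 2 cell for π1 = 95% and π0 = 90%. The sentence introducing Table 2 conflicts on power: "based on the formula above and for statistical power 90" per cent.

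**1. The plan's own figure.**
n = [(z₀.₉₇₅·√(π0(1−π0)) + z₀.₈₀·√(π1(1−π1))) / (π1−π0)]² = [(1.960×0.3000 + 0.842×0.2179)/0.05]² = 238.03, rounded up to 239. The same formula at 90% power gives 301, so 239 is the 80% figure. It contains no design effect.

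**2. Exact rule at n = 239.** The test rejects at 225 or more correct. Under independence the type I error is 1.62% and the power 78.1%. Because the test is discrete, there is some slack below 2.5%.

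**3. Within-subject clustering.** The documents give neither lesions per subject nor ICC, so both are assumed. DEFF = 1 + (Σm²/Σm − 1)×ICC, where m is the number of lesions of a subject. Beta-binomial simulation of the unadjusted rule, with ICC 0.2–0.5, gives:

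| Mean lesions per subject | Type I error |
|---|---|
| independent | 1.6% |
| 1.2 | 1.9–2.6% |
| 1.5 | 2.5–3.9% |
| 2.0 | 2.8–5.2% |

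Power is about 73–78% over these cases. The 2.5% level is passed once DEFF reaches about 1.2. At a mean of 1.1 the type I error stays at or below 2.0% even with ICC 0.5.

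The top of the range depends on how unevenly lesions are spread. At mean 2.0 and ICC 0.5, exactly two lesions each gives DEFF = 1 + (2−1)×0.5 = 1.50 and a type I error of 4.1%. Uneven sizes with Σm²/Σm = 2.5 give DEFF = 1 + 1.5×0.5 = 1.75 and 5.2%.

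To keep the planned power with a test that holds its level, n must grow to about 239×DEFF. For DEFF 1.08 that is 259; for DEFF 1.75 it is 419.

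**4. Site clustering.** With 239/30 ≈ 8 lesions per site and assumed ICC 0.01, 0.02, 0.05 and 0.10, equal sites give DEFF 1.07, 1.14, 1.35 and 1.70 and type I error 1.9%, 2.2%, 3.2% and 4.9%. Unequal sites (assumed coefficient of variation 0.83) give 2.1%, 2.7%, 4.5% and 7.5%. A mean of 1.5 lesions per subject combined with site ICC 0.02–0.05 gives 3.1–5.7%.

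**5. Is the slack dependable?** It belongs to n = 239. Under independence the exact test attains 2.43% at n = 243, 2.47% at 255 and 2.50% at 267. The synopsis says at least 239, and section 9.3.2 extends enrolment until 12 melanomas are confirmed, so the final n is not fixed.

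**6. Do the remedies hold their level?** Take independent lesions, n = 239 and π0 = 0.90:
- Identity-scale Wald test: at 223 correct, (0.9331−0.90)/√(0.9331×0.0669/239) = 2.04, so it rejects from 223. The exact type I error is 4.95%.
- Percentile bootstrap: rejects from 224, type I error 2.9%.
- Logit-scale Wald test: at 225, [ln(225/14) − ln 9]×√(225×14/239) = 0.580×3.630 = 2.10; at 224 the same statistic is 1.90. It rejects from 225, as the exact test does, with type I error 1.62%.

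With simulated within-subject clustering (means 1.2–2.0, ICC 0.2–0.5), the identity-scale robust test gave 4.8–6.6%. The logit-scale subject-clustered test gave 1.8–2.9% across two sets of runs.

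**The case against.** The best defence is that the problem may be small. Section 9.3.2 pairs about 500 lesions with up to 500 subjects and uses the two terms almost interchangeably, and the Table 1 title counts patients. Both fit a ratio near one lesion per subject. At that ratio the slack in the exact test absorbs the within-subject correlation, and if site correlation is also negligible, 239 stands. This is fair and limits the claim. It does not remove it: the plan permits several lesions per subject, sets no rule for them, and does not fix n at the value where the slack exists.

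A reader might infer that the type I error does exceed 2.5%. The documents do not support that, because every figure above 2.5% rests on an assumed number of lesions per subject and an assumed ICC, and part of the plausible range lies below 2.5%.

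A reader might also infer that the confidence interval is too narrow. The text specifies no interval for the primary endpoint, so there is nothing to call wrong. The point applies only to a binomial interval that might be reported beside the test.

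Section 9.7.3.2 defers additional analyses to a SAP that is not part of the text reviewed here. A clustered sensitivity analysis could be described there. That sentence concerns analyses beyond the stated endpoints, while the primary p-value method is already set in section 9.7.6.

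**Conclusion.** The concern holds in a conditional form. The primary test and the sample size rest on an independence assumption that the design neither secures nor justifies, so the nominal level and power are not assured. The consequence ranges from negligible, with nearly one lesion per subject and little site correlation, to a type I error of about 5% with two lesions per subject on average and ICC 0.5. Site correlation could add to this. Power under the unadjusted rule falls by at most about five percentage points over the within-subject cases considered. All of this assumes π0 = 90% and positive correlation. The matter does not undermine the study, but in a confirmatory test it should be settled before the data are analysed.

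**What to change.** Amend section 9.7.6 to adopt one of two options, before analysis:

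- **Index lesion.** Run the exact binomial test on one lesion per subject, selected by a written rule before the AI image is taken, and report all lesions as a supportive analysis. This keeps the exact test valid against within-subject correlation. The cost is fewer lesions in the primary test: 239 lesions at a mean of 1.5 per subject come from about 239/1.5 ≈ 159 subjects. The plan should say whether the 239 and the 12 melanomas then refer to index lesions.
- **All lesions.** Base the primary p-value on a subject-clustered test, with the logit scale written into the plan. Do not leave the scale open: an identity-scale Wald test or a percentile bootstrap is anti-conservative here even with independent lesions. The cost is slightly lower power, or a larger n if an ICC is assumed and the size inflated by the design effect.

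Under either option, add site clustering as a sensitivity analysis, use the chosen method for any interval reported for the primary endpoint, report the distribution of lesions per subject, and correct the Table 1 title to lesions. The lesion count and a subject identifier are already collected, so no new data are needed.
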